Statistical Analysis Plan (SAP) – Primary Analysis (APHAB)

Project: Evaluation of Unilateral vs Bilateral Hearing Aids for the Treatment of Age-related Hearing Loss

IRB Number: Pro00106077

Investigator(s): [name], AuD, PhD

Biostatistician(s): [REDACTED]

Original Creation Date: 09.21.2021

Version Date: 11.13.2024

Investigator Agreement

- All statistical analyses included in an abstract or manuscript should reflect the work of the biostatistician(s) listed on this SAP. No changes or additional analyses should be made to the results or findings without discussing with the project biostatistician(s).
- All biostatisticians on this SAP should be given sufficient time to review the full presentation, abstract, manuscript, or grant and be included as co-authors on any abstract or manuscript resulting from the analyses.
- If substantial additional analysis is necessary or the aims of the project change, a new SAP will need to be developed.
- Publications resulting from this SAP are supported in part by the Duke CTSA and must cite grant number UL1TR002553 and be submitted to PubMed Central.
- I have reviewed the SAP and understand that any changes must be documented.

Acknowledged by: Click or tap here to enter text.

Date: Click or tap to enter a date.

Activity Log

- 10.07.2021 Moved 6 month APHAB outcomes to separate SAP and edited based on feedback/comments in the 09.21.2021_SBP SAP.
- 11.01.2021 Added written models
- 01.20.2022 Edited document based on discussions
- 07.20.2022 Stratified Table 1 by randomization
- 11.17.2022 Added additional details to variables
- 12.15.2022 Edited based on discussions
- 06.28.2023 Refined ITT language
- 05.31.2024 Updated audiogram data information
- 07.11.2024 Added specific subgroup analysis (mild vs moderate)
- 09.30.2024 Added APHAB subscale change scores, specified primary analysis as “completers” analysis, changed benefit scores to change scores (3m-baseline), updated variable names, added information about adjusted models/subgroup models
- 10.28.2024 Added ineligible (missing) definition to binary APHAB change score in Section 3.2, date of data lock

11.13.2024 Moved tables to different order, removed tables for analyses we are not doing/created a subsection describing which analyses we are not doing, updated heterogeneity of treatment effects to only mention variables of interest, added variables of interest for multiple imputation

Acronyms	APHAB	Abbreviated Profile of Hearing Aid Benefit
	MoCA	Montreal Cognitive Assessment
	EC scale	Ease of Communication
	BN scale	Background Noise
	RV scale	Reverberation
	AV scale	Aversiveness

1 Study Overview

Background/Introduction: The overall goal of the project is to determine the benefit of unilateral or bilateral hearing aid fittings in adults with mild-to-moderate age-related hearing loss. This will address the lack of high-quality evidence supporting bilateral hearing aids over unilateral hearing aids. This project will use a randomized controlled trial with two treatment arms: a bilateral hearing aid fitting group and a unilateral hearing aid fitting group.

1.1 Primary Aims

- Compare the APHAB change scores between the two arms (bilateral hearing aid and unilateral hearing aid) at the end of month 3. The primary hypothesis is that bilateral hearing aids are superior to the unilateral hearing aids with respect to the overall patient-reported benefit.

1.2 Secondary Aims

- Compare the APHAB change scores between the two arms at the end of month 3 while adjusting for covariates
- Compare the APHAB change scores between the two arms at the end of month 3 with subgroup analyses
- Sensitivity analysis with missing data
- Analyze APHAB binary response at 3 months
- Create descriptives for the 4 APHAB subscales in unaided (baseline) and aided conditions (3 month) for each arm

2 Study Population

2.1 Inclusion Criteria

- 50+ years of age
- Mild to moderate, symmetrical SNHL (symmetrical: < 20 dB between ears on average from 500-4000 Hz)
- Open-mindedness to unilateral or bilateral amplification
- No prior hearing aid experience
- Adequate literacy to complete questionnaires
- Willing to purchase study-specific hearing aid(s)

2.2 Exclusion Criteria

- Concerns for middle ear pathology
- Concerns for retrocochlear pathology
- Severe tinnitus as the reason for seeking amplification
- Co-morbid condition that would interfere with study (e.g., dementia, blindness, neurologic pathology)
- History of fluctuating hearing loss

2.3 Data Acquisition

Fill in all relevant information:

Study design	Randomized controlled trial with 2 arms (bilateral hearing aid, unilateral hearing aid) Note: Randomization was stratified by clinical site.
Data source/how the data were collected	Screening information pulled from EHR data Baseline surveys captured via in-person interview and recorded in REDCap
Contact information for team member responsible for data collection/acquisition	All data access is through [REDACTED] [REDACTED]. Questions on data validity will go to PI: [name] ([contact])
Date or version (if downloaded, provide date)	Date of data pull (locked data): 10/17/2024
Data transfer method and date	Direct data extraction from REDCap
Where dataset is stored	REDCap Extracted data and analytic datasets will be stored in a secure drive on the CRU folder. Path name: \\duhs-vclin-nc1\dusom_biostats_fs\Data\BiostatsCore\CRU\Head and Neck\[name]\PCORI_Pro00106077\Data pulls

Notes: Additional variable details for all variables can be found in the "PCORI Variable Details" Excel file. Scoring details for APHAB can be found in "PCORI Scoring 20240923".

Description:

3 Outcomes, Exposures, and Additional Variables of Interest

3.1 Primary Outcome(s)

Outcome	Description	Variables and Source	Specifications
APHAB Change Score	Difference in aided APHAB scores at month 3 and unaided scores at baseline	aphab_change	Scale score – will need to calculate global communication scores at baseline (unaided) and 3 months (aided), subtract (3 months – baseline) A lower score on APHAB is better.

			
Rescore variables and multiply by 100
 
 • 1 = 0.99 • 2 = 0.87 • 3 = 0.75 • 4 = 0.50 • 5 = 0.25 • 6 = 0.12 • 7 = 0.01 
Reverse score questions 1, 9, 11, 16, 19, 21
 
Global score: mean of variables in the EC, BN, RV subscale scores (excludes questions 3, 8, 13, 17, 20, 22)
 
Note: APHAB has 4 subscales and a global communication scale. The study is powered based on the benefit score on the global communication scale (August 2019 draft – APHAB SD of 25 with different levels of Cohen's D).

--	--	--	--

3.2 Secondary Outcome(s)

Outcome	Description	Variables and Source	Specifications
APHAB change score – binary, 3 months	Responders vs non-responders for primary APHAB outcome	
Decrease of 25 units: use aphab_change_responder
 
Decrease of 15 units: use aphab_change_responder _15
	
Patients with a decrease of at least 25 units (or 15 units for the sensitivity analysis) on the APHAB scale at month 3 will be considered “responders.” Patients not returning or who do not have a score at 3 months will be considered “non-responders.” Patients with a baseline score < 25 (or < 15) are ineligible (missing).
 
Binary (25 unit decrease):
 
 • Missing if baseline score <25 • 1 if aphab_change <=-25

			
 • 0 else 
Binary (15 unit decrease);
 
 • Missing if baseline score <15 • 1 if aphab_change <=-15 • 0 else
APHAB – 4 subscales	EC, BN, RV, AV scales at both baseline and 3 months, as well as change scores	
Baseline variables:
 
aphab_ec_base aphab_bn_base aphab_rv_base aphab_av_base
 
3-month variables:
 
aphab_ec_3m aphab_bn_3m aphab_rv_3m aphab_av_3m
 
Change scores:
 
aphab_ec_change aphab_bn_change aphab_rv_change aphab_av_change
	
Rescore variables and multiply by 100
 
 • 1 = 0.99 • 2 = 0.87 • 3 = 0.75 • 4 = 0.50 • 5 = 0.25 • 6 = 0.12 • 7 = 0.01 
Reverse score questions 1, 9, 11, 16, 19, 21
 
EC: mean of questions 4, 10, 12, 14, 15, 23
 
BN: mean of questions 1, 6, 7, 16, 19, 24
 
RV: mean of questions 2, 5, 9, 11, 18, 21
 
AV: mean of questions 3, 8, 13, 17, 20, 22

3.3 Additional Variables of Interest

Variable	Description	Variables and Source	Specifications
Randomization assignment	Hearing aid assignment	assign	Binary 1: unilateral 2: bilateral
Clinical site	Which site - Duke or Vanderbilt?	which_site Character version: which_site_ch	Binary 1: Vanderbilt 2: Duke
Gender		gender Character version: gender_ch	Categorical 
 • 1: male • 2: female • 3: other • 99: declined
Age	Age at baseline (years)	age_base	Continuous

		Baseline visit is baseline_date	Years from baseline_date to dob Baseline visit is defined as aphab_base_date if non-missing, otherwise use date_moca
Race		race Character version: race_ch	Categorical 
 • 1: African American/Black • 2: White/Caucasian • 3: Asian • 4: Native American/Alaska Native • 5: Native Hawaiian/Pacific Islander • 6: More than one race • 99: Declined 
If cell counts are less than 10 for a given category, we may not report the exact cell count.
 
NIH racial categories: -American Indian/Alaska Native -Asian or Asian American -Black or African American -Native Hawaiian/Pacific Islander -White

Ethnicity		ethnicity Character version: ethnicity_ch	Categorical 
 • 1: Hispanic or Latino • 2: Not Hispanic or Latino • 999: Declined 
If cell counts are less than 10 for a given category, we may not report the exact cell count.

Income	Personal Income Last Year	income Character version: income_ch	Categorical 
 • 0: \$0 • 1: \$1 to \$9999 • 2: \$10,000 to \$24,999 • 3: \$25,000 to \$49,999 • 4: \$50,000 to \$74,999

			
 • 5: \$75,000 to \$99,999 • 6: \$100,000 to \$149,999 • 7: \$150,000 or greater • 999: Prefer not to answer 
We will also simplify this to below median/above median/prefer not to answer for heterogeneity of treatment effects

Hearing Aid Health Insurance Benefits		benefits Character version: benefits_ch	Categorical 
 • 0: No • 1: Yes • 998: Not Sure
Marital Status		marital Character version: marital_ch	Categorical 
 • 1: married • 2: widowed • 3: divorced • 4: separated • 5: never married • 999: prefer not to answer
Living arrangements		living Character version: living_ch	Categorical 
 • 1: alone • 2: with spouse • 3: with spouse and others • 888: other • 999: prefer not to answer
Education		education Character version: education_ch	Categorical 
 • 1: less than high school • 2: high school • 3: some college • 4: 4-year degree • 5: graduate degree • 888: other • 999: prefer not to answer
Baseline Date Quarter		baseline_quarter	Categorical Put baseline date into quarters
Cognition (Screened via MoCA)	Adjusted MoCA score	total_moca	Continuous, 0-30 moca31 is a modifier for high school education

			If moca31=0, then total moca score is the sum of moca1 through moca30 If moca31=1, then total moca score is the minimum of 30 and the sum of moca1 through moca 31
Audiogram Data	Frequencies: 250, 500, 750, 1000, 1500, 2000, 3000, 4000, 6000, 8000, 12000 Create a “complete” audiogram using screening and baseline data	Right ear (numeric): audio_r_250_unaided audio_r_500_unaided audio_r_750_unaided audio_r_1000_unaided audio_r_1500_unaided audio_r_2000_unaided audio_r_3000_unaided audio_r_4000_unaided audio_r_6000_unaided audio_r_8000_unaided audio_r_12000_unaided Left ear (numeric): audio_l_250_unaided audio_l_500_unaided audio_l_750_unaided audio_l_1000_unaided audio_l_1500_unaided audio_l_2000_unaided audio_l_3000_unaided audio_l_4000_unaided audio_l_6000_unaided audio_l_8000_unaided audio_l_12000_unaided NR flags right ear: audio_r_250_unaided_nr audio_r_500_unaided_nr audio_r_750_unaided_nr audio_r_1000_unaided_nr audio_r_1500_unaided_nr audio_r_2000_unaided_nr audio_r_3000_unaided_nr audio_r_4000_unaided_nr audio_r_6000_unaided_nr audio_r_8000_unaided_nr audio_r_12000_unaided_nr NR flags left ear: audio_l_250_unaided_nr audio_l_500_unaided_nr	Will create a “complete” audiogram by combining baseline and screening visit audiograms – baseline visit takes priority over screening visit. Variables are originally stored as character – can have responses like “NA”, “NR”, “DNT”. Convert to numeric. If we have any responses like this, set to missing. If “NR” – create a flag for each frequency and each ear to be 1 (0 else)

		audio_l_750_unaided_nr audio_l_1000_unaided_nr audio_l_1500_unaided_nr audio_l_2000_unaided_nr audio_l_3000_unaided_nr audio_l_4000_unaided_nr audio_l_6000_unaided_nr audio_l_8000_unaided_nr audio_l_12000_unaided_nr	
Degree of Hearing Loss – Pure Tone Average	PTA in better ear	Right ear: pta_right Left ear: pta_left Better ear: pta_better	We will use the pure tone average in the better ear. Take the average at frequencies 500, 1000, 2000, 4000 in both ears. The lower average is the better ear.
Hearing loss classification		hearing_loss_class	Binary 
 Mild: pta_better <= 40 Moderate: pta_better > 40

4 Statistical Analysis Plan

Analysis: To be completed by December 31, 2024

4.1 Demographic and Clinical Characteristics ("Table 1")

Analysis: This will be descriptive. As appropriate, we will present the mean with standard deviation (SD), median with interquartile range (IQR), and ranges (min and max), or frequency with percentage (see Table 1). Categorical variables may be collapsed into fewer categories. If cell counts are less than 10 for variables that could identify patients (e.g., race, ethnicity), we may not report the exact cell count. We may consider stratifying this table by clinical site as well.

Table 1: Patient Characteristics at Baseline

	Unilateral (N=XXX)	Bilateral (N=XXX)	Total (N=XXX)
Clinical Site			
Duke	XXX (%)	XXX (%)	XXX (%)
Vanderbilt	XXX (%)	XXX (%)	XXX (%)
Gender			
Female	XXX (%)	XXX (%)	XXX (%)
Male	XXX (%)	XXX (%)	XXX (%)
Other	XXX (%)	XXX (%)	XXX (%)
Age at Baseline Visit			
N	XXX	XXX	XXX
Missing	XXX	XXX	XXX

Mean (SD)	XXX (XXX)	XXX (XXX)	XXX (XXX)
Median	XXX	XXX	XXX
Q1, Q3	XXX , XXX	XXX , XXX	XXX , XXX
Range	XXX - XXX	XXX - XXX	XXX - XXX
Race			
American Indian/Alaska Native	XXX (%)	XXX (%)	XXX (%)
Asian	XXX (%)	XXX (%)	XXX (%)
Black or African American	XXX (%)	XXX (%)	XXX (%)
White	XXX (%)	XXX (%)	XXX (%)
More than one race	XXX (%)	XXX (%)	XXX (%)
Native Hawaiian/Pacific Islander	XXX (%)	XXX (%)	XXX (%)
Declined	XXX (%)	XXX (%)	XXX (%)
Ethnicity			
Hispanic or Latino	XXX (%)	XXX (%)	XXX (%)
Not Hispanic or Latino	XXX (%)	XXX (%)	XXX (%)
Declined	XXX (%)	XXX (%)	XXX (%)
Personal Income Last Year			
\$0	XXX (%)	XXX (%)	XXX (%)
\$1 to \$9999	XXX (%)	XXX (%)	XXX (%)
\$10,000 to \$24,999	XXX (%)	XXX (%)	XXX (%)
\$25,000 to \$49,999	XXX (%)	XXX (%)	XXX (%)
\$50,000 to \$74,999	XXX (%)	XXX (%)	XXX (%)
\$75,000 to \$99,999	XXX (%)	XXX (%)	XXX (%)
\$100,000 to \$149,999	XXX (%)	XXX (%)	XXX (%)
\$150,000 or greater	XXX (%)	XXX (%)	XXX (%)
Prefer not to answer	XXX (%)	XXX (%)	XXX (%)
Personal Income Last Year (Categorical)			
Below Median	XXX (%)	XXX (%)	XXX (%)
Above Median	XXX (%)	XXX (%)	XXX (%)
Prefer not to answer	XXX (%)	XXX (%)	XXX (%)
Hearing Aid Health Insurance Benefits			
No	XXX (%)	XXX (%)	XXX (%)
Yes	XXX (%)	XXX (%)	XXX (%)
Not sure	XXX (%)	XXX (%)	XXX (%)
Marital Status			
Married	XXX (%)	XXX (%)	XXX (%)
Widowed	XXX (%)	XXX (%)	XXX (%)
Divorced	XXX (%)	XXX (%)	XXX (%)
Separated	XXX (%)	XXX (%)	XXX (%)
Never married	XXX (%)	XXX (%)	XXX (%)
Prefer not to answer	XXX (%)	XXX (%)	XXX (%)
Living Arrangements			
Alone	XXX (%)	XXX (%)	XXX (%)
With spouse	XXX (%)	XXX (%)	XXX (%)

With spouse and others	XXX (%)	XXX (%)	XXX (%)
Other	XXX (%)	XXX (%)	XXX (%)
Prefer not to answer	XXX (%)	XXX (%)	XXX (%)
Education			
Less than high school	XXX (%)	XXX (%)	XXX (%)
High school	XXX (%)	XXX (%)	XXX (%)
Some college	XXX (%)	XXX (%)	XXX (%)
4-year degree	XXX (%)	XXX (%)	XXX (%)
Graduate degree	XXX (%)	XXX (%)	XXX (%)
Other	XXX (%)	XXX (%)	XXX (%)
Quarter of Baseline Visit			
2021 Q2	XXX (%)	XXX (%)	XXX (%)
2021 Q3	XXX (%)	XXX (%)	XXX (%)
2021 Q4	XXX (%)	XXX (%)	XXX (%)
...	XXX (%)	XXX (%)	XXX (%)
Total MoCA Score			
N	XXX	XXX	XXX
Missing	XXX	XXX	XXX
Mean (SD)	XXX (XXX)	XXX (XXX)	XXX (XXX)
Median	XXX	XXX	XXX
Q1, Q3	XXX , XXX	XXX , XXX	XXX , XXX
Range	XXX - XXX	XXX - XXX	XXX - XXX
Pure Tone Average in Better Ear**			
N	XXX	XXX	XXX
Missing	XXX	XXX	XXX
Mean (SD)	XXX (XXX)	XXX (XXX)	XXX (XXX)
Median	XXX	XXX	XXX
Q1, Q3	XXX , XXX	XXX , XXX	XXX , XXX
Range	XXX - XXX	XXX - XXX	XXX - XXX
Hearing Loss Classification in Better Ear			
Mild	XXX (%)	XXX (%)	XXX (%)
Moderate	XXX (%)	XXX (%)	XXX (%)

(report generated on XXXXXXXX)

**Average value for frequencies of 500, 1000, 2000, 4000 Hz

We will create a table for clinical characteristics (Supplemental Table 1) which will be given to [name] in order to create an audiogram that follows the standards of the field.

Supplemental Table 1: Clinical Characteristics at Baseline

	Unilateral (N=XXX)	Bilateral (N=XXX)	Total (N=XXX)
Right Ear: 250 Hz			
N	XXX	XXX	XXX
Mean (SD)	XXX (XXX)	XXX (XXX)	XXX (XXX)
NR Values	XXX	XXX	XXX
Right Ear: 500 Hz			
N	XXX	XXX	XXX
Mean (SD)	XXX (XXX)	XXX (XXX)	XXX (XXX)
NR Values	XXX	XXX	XXX
Right Ear: 750 Hz			
N	XXX	XXX	XXX
Mean (SD)	XXX (XXX)	XXX (XXX)	XXX (XXX)
NR Values	XXX	XXX	XXX
Right Ear: 1000 Hz			
N	XXX	XXX	XXX
Mean (SD)	XXX (XXX)	XXX (XXX)	XXX (XXX)
NR Values	XXX	XXX	XXX
Right Ear: 1500 Hz			
N	XXX	XXX	XXX
Mean (SD)	XXX (XXX)	XXX (XXX)	XXX (XXX)
NR Values	XXX	XXX	XXX
Right Ear: 2000 Hz			
N	XXX	XXX	XXX
Mean (SD)	XXX (XXX)	XXX (XXX)	XXX (XXX)
NR Values	XXX	XXX	XXX
Right Ear: 3000 Hz			
N	XXX	XXX	XXX
Mean (SD)	XXX (XXX)	XXX (XXX)	XXX (XXX)
NR Values	XXX	XXX	XXX
Right Ear: 4000 Hz			
N	XXX	XXX	XXX
Mean (SD)	XXX (XXX)	XXX (XXX)	XXX (XXX)
NR Values	XXX	XXX	XXX
Right Ear: 6000 Hz			
N	XXX	XXX	XXX
Mean (SD)	XXX (XXX)	XXX (XXX)	XXX (XXX)
NR Values	XXX	XXX	XXX
Right Ear: 8000 Hz			
N	XXX	XXX	XXX
Mean (SD)	XXX (XXX)	XXX (XXX)	XXX (XXX)
NR Values	XXX	XXX	XXX
Right Ear: 12000 Hz			

N	XXX	XXX	XXX
Mean (SD)	XXX (XXX)	XXX (XXX)	XXX (XXX)
NR Values	XXX	XXX	XXX
Left Ear: 250 Hz			
N	XXX	XXX	XXX
Mean (SD)	XXX (XXX)	XXX (XXX)	XXX (XXX)
NR Values	XXX	XXX	XXX
Left Ear: 500 Hz			
N	XXX	XXX	XXX
Mean (SD)	XXX (XXX)	XXX (XXX)	XXX (XXX)
NR Values	XXX	XXX	XXX
Left Ear: 750 Hz			
N	XXX	XXX	XXX
Mean (SD)	XXX (XXX)	XXX (XXX)	XXX (XXX)
NR Values	XXX	XXX	XXX
Left Ear: 1000 Hz			
N	XXX	XXX	XXX
Mean (SD)	XXX (XXX)	XXX (XXX)	XXX (XXX)
NR Values	XXX	XXX	XXX
Left Ear: 1500 Hz			
N	XXX	XXX	XXX
Mean (SD)	XXX (XXX)	XXX (XXX)	XXX (XXX)
NR Values	XXX	XXX	XXX
Left Ear: 2000 Hz			
N	XXX	XXX	XXX
Mean (SD)	XXX (XXX)	XXX (XXX)	XXX (XXX)
NR Values	XXX	XXX	XXX
Left Ear: 3000 Hz			
N	XXX	XXX	XXX
Mean (SD)	XXX (XXX)	XXX (XXX)	XXX (XXX)
NR Values	XXX	XXX	XXX
Left Ear: 4000 Hz			
N	XXX	XXX	XXX
Mean (SD)	XXX (XXX)	XXX (XXX)	XXX (XXX)
NR Values	XXX	XXX	XXX
Left Ear: 6000 Hz			
N	XXX	XXX	XXX
Mean (SD)	XXX (XXX)	XXX (XXX)	XXX (XXX)
NR Values	XXX	XXX	XXX
Left Ear: 8000 Hz			
N	XXX	XXX	XXX
Mean (SD)	XXX (XXX)	XXX (XXX)	XXX (XXX)
NR Values	XXX	XXX	XXX
Left Ear: 12000 Hz			

N	XXX	XXX	XXX
Mean (SD)	XXX (XXX)	XXX (XXX)	XXX (XXX)
NR Values	XXX	XXX	XXX

(report generated on XXXXXXX)

4.2 Describe APHAB Global Score Distributions and Responder Status

We will describe the distribution of APHAB global score at baseline (unaided) and 3 months (aided), along with the change score and responder status (both definitions) by hearing aid assignment in Table 2.

Table 2: APHAB Global Score Distributions and Responder Status

	Unilateral (N=XXX)	Bilateral (N=XXX)	Total (N=XXX)
APHAB Global Score (Baseline)			
N	XXX	XXX	XXX
Missing	XXX	XXX	XXX
Mean (SD)	XXX (XXX)	XXX (XXX)	XXX (XXX)
Median	XXX	XXX	XXX
Q1, Q3	XXX , XXX	XXX , XXX	XXX , XXX
Range	XXX - XXX	XXX - XXX	XXX - XXX
APHAB Global Score (3 Months)			
N	XXX	XXX	XXX
Missing	XXX	XXX	XXX
Mean (SD)	XXX (XXX)	XXX (XXX)	XXX (XXX)
Median	XXX	XXX	XXX
Q1, Q3	XXX , XXX	XXX , XXX	XXX , XXX
Range	XXX - XXX	XXX - XXX	XXX - XXX
APHAB Change Score			
N	XXX	XXX	XXX
Missing	XXX	XXX	XXX
Mean (SD)	XXX (XXX)	XXX (XXX)	XXX (XXX)
Median	XXX	XXX	XXX
Q1, Q3	XXX , XXX	XXX , XXX	XXX , XXX
Range	XXX - XXX	XXX - XXX	XXX - XXX
APHAB Responder (25 Units)*			
No	XXX (%)	XXX (%)	XXX (%)
Yes	XXX (%)	XXX (%)	XXX (%)
Ineligible to Drop 25 Units	XXX	XXX	XXX
APHAB Responder (15 Units)*			
No	XXX (%)	XXX (%)	XXX (%)
Yes	XXX (%)	XXX (%)	XXX (%)
Ineligible to Drop 15 Units	XXX	XXX	XXX

*Denominator for percentages does not include patients ineligible to drop 'X' units

4.3 Primary aim: compare APHAB scores between the two arms

Compare the APHAB change scores between the two arms (bilateral hearing aid and unilateral hearing aid) at the end of month 3 vs baseline.

Analysis: This will be done for all randomized patients who have both baseline and 3 month scores (a “completers” analysis). The primary analysis will be performed by linear regression and include randomized assignment and clinical site as covariates.

$$APHAB \text{ change score} = \beta_0 + \beta_1 * \text{treatment} + \beta_2 * \text{site}$$

Table 3: Linear Regression Beta Estimates
Outcome Modelled: APHAB Change Score

Covariate	Beta	95% C.I.	P-Value*
Hearing Aid Assignment (Reference: Bilateral)			
Unilateral	XXX	(XXX , XXX)	XXX
Clinical Site (Reference: Duke)			
Vanderbilt	XXX	(XXX , XXX)	XXX

*Using XXX statistic

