4.4 Heterogeneity of Treatment Effects Analysis for APHAB scores

Compare APHAB change scores between the two arms at the end of month 3 vs baseline while adjusting for interaction terms between treatment and each variable of interest.

Analysis: This will be done for all randomized patients who have both baseline and 3 month scores (“completers”). The primary analysis will be performed by linear regression and include randomized assignment, clinical site, a given variable of interest (denoted by S), and interactions between treatment and the variable of interest, with separate models fit for each variable of interest. The two variables of interest that decided to investigate are income group (simplified version – below median, above median, prefer not to answer) and hearing loss classification (mild, moderate). Interactions will be tested at the 0.15 level. If the overall test for the interaction is significant, forest plots will be constructed to examine the heterogeneity of treatment effect and formal treatment by factor interaction terms tested in the models. The general model structure is:

$$APHAB \text{ change score} = \beta_0 + \beta_1 * \text{treatment} + \beta_2 * \text{site} + \beta_S * S + \beta_{ST} * S * \text{treatment}$$

Table 4: Linear Regression Beta Estimates for Variable S Model
Outcome Modelled: APHAB Change Score

Covariate	Beta	95% C.I.	P-Value*
Hearing Aid Assignment (Reference: Bilateral)			
Unilateral	XXX	(XXX , XXX)	XXX
Clinical Site (Reference: Duke)			
Vanderbilt	XXX	(XXX , XXX)	XXX
Variable S	XXX	(XXX, XXX)	XXX
HA Assignment*Variable S	XXX	(XXX, XXX)	XXX

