4.5 Sensitivity analyses for APHAB scores

If more than 5% of randomized patients have missing APHAB scores at 3 months, we will use multiple imputation in an intent to treat sensitivity analysis.

Analysis 1: An imputation model via linear regression will be developed based on available data and will include initial APHAB scores, treatment, baseline characteristics, and possible interactions of these variables with treatment. The specific variables of interest to include are: treatment, site, income group, and baseline APHAB. A total of 1000 datasets with imputations of APHAB score reduction will be generated using this model. Each dataset will be analyzed using linear regression models as described in section 4.3. The combined results will be reported and will take the variability of multiple imputations into account.

Analysis 2: The characteristics from the participants with completed data will be compared to those with missing APHAB data with the use of a “Table 1”. We may also include treatment randomization in this table.

Table 5: Patient Characteristics for Missing and Non-Missing APHAB

	Missing APHAB (N=XXX)	Not Missing APHAB (N=XXX)	Total (N=XXX)
Assignment			
Unilateral	XXX (%)	XXX (%)	XXX (%)
Bilateral	XXX (%)	XXX (%)	XXX (%)
Clinical Site			
Duke	XXX (%)	XXX (%)	XXX (%)
Vanderbilt	XXX (%)	XXX (%)	XXX (%)
Gender			
Female	XXX (%)	XXX (%)	XXX (%)
Male	XXX (%)	XXX (%)	XXX (%)
Other	XXX (%)	XXX (%)	XXX (%)
Age at Baseline Visit			
N	XXX	XXX	XXX
Missing	XXX	XXX	XXX
Mean (SD)	XXX (XXX)	XXX (XXX)	XXX (XXX)
Median	XXX	XXX	XXX
Q1, Q3	XXX , XXX	XXX , XXX	XXX , XXX
Range	XXX - XXX	XXX - XXX	XXX - XXX
Race			
American Indian/Alaska Native	XXX (%)	XXX (%)	XXX (%)
Asian	XXX (%)	XXX (%)	XXX (%)
Black or African American	XXX (%)	XXX (%)	XXX (%)
White	XXX (%)	XXX (%)	XXX (%)
More than one race	XXX (%)	XXX (%)	XXX (%)
Native Hawaiian/Pacific Islander	XXX (%)	XXX (%)	XXX (%)
Declined	XXX (%)	XXX (%)	XXX (%)
Ethnicity			

Hispanic or Latino	XXX (%)	XXX (%)	XXX (%)
Not Hispanic or Latino	XXX (%)	XXX (%)	XXX (%)
Declined	XXX (%)	XXX (%)	XXX (%)
Personal Income Last Year			
\$0	XXX (%)	XXX (%)	XXX (%)
\$1 to \$9999	XXX (%)	XXX (%)	XXX (%)
\$10,000 to \$24,999	XXX (%)	XXX (%)	XXX (%)
\$25,000 to \$49,999	XXX (%)	XXX (%)	XXX (%)
\$50,000 to \$74,999	XXX (%)	XXX (%)	XXX (%)
\$75,000 to \$99,999	XXX (%)	XXX (%)	XXX (%)
\$100,000 to \$149,999	XXX (%)	XXX (%)	XXX (%)
\$150,000 or greater	XXX (%)	XXX (%)	XXX (%)
Prefer not to answer	XXX (%)	XXX (%)	XXX (%)

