4.8 Initially planned analyses that we will not do

We had initially planned to conduct adjusted analyses for the outcomes of global change score and both responder definitions. After reviewing cell counts of demographics at baseline and discussion, we decided that there are no variables of interest to include in an adjusted model.

Statistical Analysis Plan (SAP) – Secondary (3-Month) Outcomes and Descriptives

Project: Evaluation of Unilateral vs Bilateral Hearing Aids for the Treatment of Age-related Hearing Loss

IRB Number: Pro00106077

Investigator(s): [name], AuD, PhD

Biostatistician(s): [name], [name], [name]

Original Creation Date: 12.15.2021

Version Date: 09.30.2024

Investigator Agreement

- All statistical analyses included in an abstract or manuscript should reflect the work of the biostatistician(s) listed on this SAP. No changes or additional analyses should be made to the results or findings without discussing with the project biostatistician(s).
- All biostatisticians on this SAP should be given sufficient time to review the full presentation, abstract, manuscript, or grant and be included as co-authors on any abstract or manuscript resulting from the analyses.
- If substantial additional analysis is necessary or the aims of the project change, a new SAP will need to be developed.
- Publications resulting from this SAP are supported in part by the Duke CTSA and must cite grant number UL1TR002553 and be submitted to PubMed Central.
- I have reviewed the SAP and understand that any changes must be documented.

Acknowledged by: Click or tap here to enter text.

Date: Click or tap to enter a date.

Activity Log

- 11.16.2023 Split secondary outcomes SAP into multiple SAPs
- 05.31.2024 Added additional variables
- 07.11.2024 Resolved some questions about variables (see SAP dated 20240531 and Overview of All Planned Analysis dated 20240620)
- 07.25.2024 Moved GHABP from the GHABP/EMA SAP to this SAP
- 09.30.2024 Updated variable names, resolved comments from previous SAP dated 20240725)

Acronyms

APHAB	Abbreviated Profile of Hearing Aid Benefit
EMA	Ecological Momentary Assessment
GHABP	Glasgow Hearing Aid Benefit Profile
IOI-HA	International Outcomes Inventory for Hearing Aids
SADL	Satisfaction with Amplification in Daily Life
SSQ	Speech Spatial Qualities
HHIE	Hearing Handicap Inventory for Elderly

1 Study Overview

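### The primary APHAB model leaves out baseline APHAB; adding it would narrow the primary 95% CI by about 8% to 19% if the baseline-to-month-3 correlation is 0.7 to 0.3 and the two SDs are equal

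*SAP*

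**What the plan says.** All sections cited are in the primary APHAB SAP unless stated.

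- **Primary model (4.3).** "The primary analysis will be performed by linear regression and include randomized assignment and clinical site as covariates". The equation and Table 3 agree: an intercept, arm and site. The outcome (3.1) is the aided month-3 global score minus the unaided baseline score.
- **Analysis set (4.3).** "This will be done for all randomized patients who have both baseline and 3 month scores".
- **Other comparisons of APHAB between arms.** The heterogeneity models (4.4) add one factor and its interaction with arm: "The primary analysis will be performed by linear regression and include randomized assignment, clinical site, a given variable of interest". That factor is income group or hearing-loss class. The responder models (4.6) have the same structure. None contains baseline APHAB as a covariate.
- **Imputation (4.5).** "The specific variables of interest to include are: treatment, site, income group, and baseline APHAB". The imputed datasets are then analysed with the 4.3 model, which drops baseline again.
- **Adjusted analyses.** Section 1.2 lists as an aim: "Compare the APHAB change scores between the two arms at the end of month 3 while adjusting for covariates". Section 4.8 withdraws it: "After reviewing cell counts of demographics at baseline and discussion, we decided that there are no variables of interest".
- **Power (3.1).** "The study is powered based on the benefit score on the global communication scale", with an APHAB SD of 25.
- **Timing (2.3).** "Date of data pull (locked data): 10/17/2024". The SAP version date is 11.13.2024.

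**The concern.** Regressing change on arm and site is the same as regressing the month-3 score on arm, site and baseline with the baseline coefficient forced to 1. If the true coefficient is below 1, subtracting the whole baseline score puts avoidable noise into the outcome and over-corrects any chance baseline difference between arms. Estimating the coefficient removes that noise.

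What is at stake is precision in the primary comparison. The interval is wider than the collected data require, and the loss repeats in 4.5 and 4.4, which build on the same model.

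The reason recorded in 4.8 does not cover this covariate. Sparse demographic cells are no argument against a continuous score that is complete in the analysis set. The text does not say whether baseline APHAB was ever a candidate.

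**Working it through.** **No figure to reproduce.** The documents state no target difference, power, alpha or expected interval width for the primary test. For orientation only, 350 patients (protocol section 6) with SD 25 fit a difference of 0.30 SD at 80% power, which needs 350. They fit 0.35 SD at 90% power almost as well, which needs 344. The design point cannot be identified.

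**Inputs**
- From the documents: 350 patients; 1:1 allocation (protocol section 4), so 175 per arm; SD 25 (SAP 3.1); 95% CI (Table 3).
- Assumed: correlation ρ between baseline and month-3 scores of 0.3 to 0.7; ratio k of month-3 SD to baseline SD of 0.8 to 1.2, since one score is unaided and the other aided; 25 is the SD of change, which 3.1 does not say outright; all 350 analysed; two-sided 0.05.

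**Formulas**, with baseline SD s:
- Variance of change: s²(1 + k² − 2ρk)
- Residual variance with baseline in the model: s²k²(1 − ρ²)
- Ratio R = k²(1 − ρ²) / (1 + k² − 2ρk), which is (1 + ρ)/2 when k = 1
- CI narrowing = 1 − √R; equivalent sample size = 350/R

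At ρ = 0.5 and k = 1: R = 0.75, narrowing = 1 − √0.75 = 13.4%, equivalent N = 350/0.75 = 467.

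| k | ρ | R | CI narrower by | Equivalent N |
|---|---|---|---|---|
| 0.8 | 0.3 | 0.50 | 29.1% | 697 |
| 0.8 | 0.5 | 0.57 | 24.4% | 612 |
| 0.8 | 0.7 | 0.63 | 20.8% | 558 |
| 1.0 | 0.3 | 0.65 | 19.4% | 538 |
| 1.0 | 0.5 | 0.75 | 13.4% | 467 |
| 1.0 | 0.7 | 0.85 | 7.8% | 412 |
| 1.2 | 0.3 | 0.76 | 12.7% | 459 |
| 1.2 | 0.5 | 0.87 | 6.7% | 402 |
| 1.2 | 0.7 | 0.97 | 1.7% | 362 |

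The narrowing does not depend on SD 25, on N or on dropout.

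**Absolute scale, if 25 is the SD of change.** The current SE is 25 × √(2/175) = 2.67. With baseline added it is 2.15 to 2.46 at k = 1, and 1.89 to 2.63 over the grid. The current model detects 7.5 units with 80% power. At that difference the adjusted model has 94% to 86% power at k = 1, and 98% to 81% over the grid. With 10% dropout (315 completers) the SE is 2.82 now and 2.00 to 2.77 adjusted.

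**Chance imbalance.** The true slope is ρk, so each unit of baseline difference between arms moves the change-score estimate by 1 − ρk relative to the adjusted estimate, in the direction opposite to the imbalance. Over the grid this is 0.16 to 0.76 units. The implied baseline SD is 25/√(1 + k² − 2ρk) = 19.1 to 34.7, so a one-SE imbalance is 2.0 to 3.7 units and moves the estimate by 0.5 to 1.9 units.

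**Simulation.** With 4,000 trials per setting, 350 patients, and arm and site in both models, type I error was 4.6% to 5.5% for both. Both recovered a true difference of −7.5 (mean estimates −7.43 to −7.59). A separate set of 1,500 trials per setting gave mean narrowing of 19.2%, 13.2% and 7.7% at k = 1, and 29.0% and 1.6% at the two extremes, in line with the formula.

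**Is a slope of 1 plausible?** Section 4.6 excludes patients with baseline below 25 from the 25-unit responder analysis because they cannot fall that far. The SAP therefore recognises that possible change depends on baseline, which argues against a slope of exactly 1.

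**The case against.** The strongest objection is timing. The lock preceded the current SAP version, section 4 set completion of the analysis for December 31, 2024, and the 6-month SAP of 01.07.2025 already refers to switching behaviour at 3 months. The documents do not say whether arm-level APHAB results had been seen. If they had, changing the primary model costs prespecification, and baseline adjustment can only stand beside the planned analysis. This stands, and the fix allows for it. On the other side, the activity log shows adjusted models still in the plan on 09.30.2024, before the lock; they were withdrawn on 11.13.2024, after it.

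Second, the size of the gain is assumed. That also stands. The grid is not a bound: the gain is nil at ρ = 0.9 and k = 1.1, and 37.5% at ρ = 0 and k = 0.8. The absolute figures are weaker than the ratios. At ρ = 0.7, an SD of change of 25 implies a baseline SD of about 29 to 35. A uniform spread over the 1 to 99 scoring range has an SD of only 98/√12 = 28.3, so that corner is doubtful for an 18-item mean. If the design point was 0.35 SD at 90% power, the gain at k = 1 is from 90% to about 94% to 98%.

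Third, chance imbalance is not a second harm. Its variation is already inside the change-score SE, the shift is below one SE (2.67), and Table 2 shows baseline by arm. This is right: it is the same loss seen within a single trial.

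Fourth, 4.8 also cites discussion, and the entry left in 1.2 is editorial. Both are fair, but the content of the discussion is not recorded, so no reason for omitting baseline APHAB is on file.

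**Conclusion.** The concern holds as one of efficiency. The planned analysis is valid, and it matches the score on which the study was powered. It forgoes precision that the collected data would supply: 8% to 19% of CI width for ρ of 0.7 to 0.3 with equal SDs, and 2% to 29% if k may run from 0.8 to 1.2. The algebra is certain; the size depends on ρ and k, which the documents do not give. The gain vanishes as ρk approaches 1. Apart from one degree of freedom, there is no expected loss of precision anywhere. The effect being estimated does not change. The change is worth making but is not essential to the validity of the trial.

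**What to change.** 1. Make the primary model: APHAB change = β0 + β1·treatment + β2·site + β3·baseline APHAB global score, with baseline continuous. Using the month-3 score as outcome gives the same treatment estimate.
2. Use this model for the imputed datasets in 4.5, and add the baseline term to the models in 4.4.
3. Keep the current model as a supportive analysis.
4. Date the change and state whether arm-level results had been seen. If they had, keep the current model as primary, report the adjusted model beside it and label it post hoc.
5. Reconcile 1.2 with 4.8, and record in 4.8 how baseline APHAB was considered.
6. Leave the responder models as planned. Any baseline-adjusted version should be supportive and labelled as a conditional odds ratio, because adjustment changes what an odds ratio estimates.

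The cost is one covariate in text and code, plus a dated post-lock amendment. No new data are needed and no completer is lost from 4.3. The 4.4 models use the same completers, and the imputation model already requires baseline APHAB.
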